B. *Wide variations in disparity highlight uncertainty.* Careful literature review documents that disparities in health services related to disability are complex and sometimes not consistent. Although PWD consistently receive fewer preventive services such as dental care, mammograms, or fecal occult blood tests compared to PWOD with the same chronic conditions, practice patterns vary. Our preliminary studies found that people with mild disabilities were more likely to receive influenza vaccines than PWOD, while those with the most severe disabilities experiencing the greatest need and the greatest access barriers were less likely vaccinated. These inconsistencies may relate to greater medical needs interacting with hampered abilities to obtain services.

C. *Policy change can benefit populations.* Potentially preventable hospitalizations for certain conditions are declining in the general population suggesting improvements in ambulatory care. Greater access to community health centers, rural health clinics, Medicaid Managed Care, Health Maintenance Organizations, and implementation of Medicare Part D with increased drug coverage have been linked to reduced hospitalizations. Having a regular place of care is associated with receipt of better prevention. This suggests that policies supporting greater access to ambulatory care may be improving population health. If access disparities are severe among PWD, that sub-population may be excluded from these benefits.

D. *Importance to patients or caregivers:* The Institute of Medicine's (IOM) September 2012 report, "Best Care at Lower Cost," calls for improving "capacity to capture clinical, care delivery processes" and achieving "better care, system improvement and the generation of new knowledge." PWD, family members, and healthcare providers partnering with researchers who will analyze a decade of records from the ongoing Medicare Current Beneficiary Survey (MCBS) about clinical and care delivery processes will be partnering to develop the ecologically valid **Patient-Informed Surveillance Tool.** This Tool will have the potential to improve the

PRINCIPAL INVESTIGATOR (LAST, FIRST, MIDDLE): [name]

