#### **Choice of data for quantitative analyses and Description of Data Sources**

The MCBS is conducted by the Centers for Medicare and Medicaid Services (CMS) through in-person beneficiary or proxy interviews. Respondents are sampled from the Medicare enrollment file to be representative of the Medicare population as a whole. Sample persons are interviewed three times a year for a maximum of four years forming a continuous profile of each individual's personal health care experience. Aims 2, 3, and 4 will apply a decade of data from the MCBS. The MCBS sample was selected for the qualitative aspects of Aims 2, 3, and 4 because these data provide the means to quantify the prevalence of disparities within the Medicare population and any associated outcome burden at the societal level. Also, derivation of the **Patient-Informed Surveillance Tool** within MCBS data will facilitate its potential implementation within Medicare as a means to monitor disparities and outcomes. The oldest old (80 and over) and the young disabled (between the ages of 21 and 64) are oversampled to permit more detailed analyses of these sub-populations. The MCBS applies a rotating panel survey design. A rotating panel will be followed for 12 interviews. There are four panels active at any one time. Each has approximately 4,000 sample persons. New panels introduced each year in the fall round will replace the oldest panel retired the following summer. This project will use the Access to Care files from the MCBS which include all variables needed in the analyses.

**The Study Sample:** An Access to Care file is released within 2 years of the survey. We plan to request 10 panels entering at the time of their fall interview in 2000-2009. Access to Care files in the following 3 fall interviews (2010-2012) will serve to track 1, 2, and 3 year transition outcomes. The sample will include all fee for service and Health Maintenance Organization (HMO) Medicare beneficiaries 21 years of age and older. Those living in institutions at the time of their initial interviews will not be included since institutionalization is an outcome state.

**1. Variable Definition and Measurement (Quantitative).** All variables are available in the MCBS Access to Care files.

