Activity Limitation Stages determined during the baseline fall interview will be the key independent variable (see Table 1 for definitions). ADL stages (0-IV) will be primary and IADL stages (0-IV) analyzed secondarily. IADLs such as meal preparation are not always relevant when someone else is available to perform those tasks, yet IADL enables exploration of the effects of milder disabilities.

Other covariates: *Working age* 21 to 64 and 65 and over; *gender*; *race* (African American or Black, Hispanic, White, and other); *education* (high school graduation Y/N); *marital status* (married/unmarried); *income* (Medicare categories of annual household income from all sources); *insurance type* (Medicare only, Medicare and Medicaid-dual enrollee, private-supplemental, other (i.e., Champus, VA)); *living arrangement* (i.e., lives alone or with spouse only, with children, with other relatives or non-relatives, or in a retirement community); and the *presence or absence of accessibility features in the home* (home accessibility features). Health status will be captured by physician-reported *chronic conditions and impairments* (hypertension, asthma, diabetes, COPD, coronary artery disease, and congestive heart failure, intellectual and/or developmental disability, dementia or Alzheimer’s disease, neurological disorders, mental illness, no usable vision, and deaf). Building on our previous work, we know that the nature and severity of disabilities resulting from these conditions can be expected to vary. As example, neuropsychiatric conditions, particularly those causing intellectual disabilities, are often extremely disabling, while people who are blind or deaf often find ways to accommodate and perform basic activities. Analyses will control for residence based on Census regions.

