#### Data Analysis

Complex survey design: The MCBS uses a multi-stage clustering sample with unequal sampling probabilities. We will take into account the complex design by using appropriate survey commands in Stata to calculate the correct point estimates and their variances. Specifically, the set of longitudinal weights (RIC X2) allowing analysis of data trends over a two year period and a second set of longitudinal weights (RIC X3) will be applied to two- and three-year outcomes.

Proxies: Proxy responses will be included in all models. About 9.8% of MCBS baseline interviews were conducted by proxies and our previous work indicates that exclusion of proxy responses results in underestimates of disability prevalence. Recognizing this may explain proxy differences we will explore replacing proxy status with reason for proxy use.

Missing data and attrition: See Avoidance of Bias below.

General approach to analysis: Each Aim will describe the sample of Medicare beneficiaries with weighted uni-variable summary statistics appropriate to the distributional characteristics of the variables of interest and bi-variable associations with outcomes. Because of concerns that some variables may be intermediate on causal pathways, to understand associations, we will build etiological models hierarchically. All will control for baseline age, gender, race, ADL or

PRINCIPAL INVESTIGATOR (LAST, FIRST, MIDDLE): [name]

IADL stage, and proxy status. Health conditions and living circumstances will be added sequentially, selected according to associations with functional change, institutionalization, or mortality or according to emergent themes from stakeholder groups. The Goodness-of-Fit (GOF), Deviance and Pearson GOF Statistic, ROC curve, and r-square values as appropriate to each regression will be reported to document model fit of the multinomial regressions. Stata 11.0 (Stata Corp, College Station, Texas) will be used for all analyses (except for multiple imputation as noted below). A 2-sided  $p<.05$  will be used for all final tests of significance.

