The quantitative analytic team under the direction of [name] is highly experienced in population-level analyses of PWD as well as in the use of qualitative and quantitative merge designs. The analytic protocol will include weekly meetings of [name] and all team members, with consultants and subcontractors joining at key times in formulating linkages between the qualitative findings and its use in informing the evidence-based findings. Formal agendas will be disseminated by email, followed by minutes which are jointly produced by [name] and [name] (project manager). Our extensive preliminary work with MCBS data highlights the time and careful analyses required to prepare the data. Because final analyses require merging across multiple years, and not all that data will be available the first study year, analyses for all Aims will continue cyclically. We will program for table shell development, building in additional data as it becomes available over the years (see project timeline). No cell size of less than 11 persons will be analyzed or reported. Since each of the 10 entry cohorts will be formulated the same way, we will be able to use the early data waves to form analytic files which will be appended over the study years. Thus, Aims 2, 3, and 4 have both early and late phases.

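### Ten entry panels and both fee-for-service and HMO members are pooled, but the covariate set has no entry-year term and no HMO level; the confounding is avoidable and probably small

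*Combined protocol and SAP*

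**What the plan says.** Under The Study Sample the plan states "We plan to request 10 panels entering at the time of their fall interview in 2000-2009", and then "The sample will include all fee for service and Health Maintenance Organization (HMO) Medicare beneficiaries 21 years of age and older". The Project Plan and Timeline describes how the cohorts are joined: "Since each of the 10 entry cohorts will be formulated the same way, we will be able to use the early data waves", with later waves appended as they arrive.

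The covariates are itemised under Other covariates. Insurance type has four levels: "Medicare only, Medicare and Medicaid-dual enrollee, private-supplemental, other (i.e., Champus, VA". The paragraph ends with geography: "Analyses will control for residence based on Census regions". The rest of the list is age group, gender, race, education, marital status, income, living arrangement, home accessibility and chronic conditions.

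Under Data Analysis, the general approach fixes what enters every model: "All will control for baseline age, gender, race, ADL or" IADL stage, and proxy status. Health conditions and living circumstances "will be added sequentially, selected according to associations with functional change, institutionalization, or mortality", or because stakeholder groups raise them.

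In the background section on innovation, the plan lists "Health Maintenance Organizations, and implementation of Medicare Part D" among the developments associated with fewer hospitalizations.

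**The concern.** The pooled file spans ten entry years and two ways of receiving Medicare, yet the models treat it as one homogeneous cohort. If dissatisfaction drifted over the decade while mortality or institutionalization also drifted, part of that shared drift would appear in the comparator coefficients. The same holds if HMO members differ from fee-for-service members in both respects. The Access comparator is the most exposed: it has three items, one of them out-of-pocket cost, which coverage could plausibly move.

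The coefficients matter beyond Aim 3. Aim 4 uses them to compare hypothetical policies, one comparator at a time, so any period or plan effect absorbed by a comparator would be presented as benefit available from improving it.

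**Working it through.** **1. Is either term supplied anywhere?** Each place that could supply one, in turn:

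- Other covariates: no panel, entry year or calendar time; four insurance levels, none for HMO or managed care.
- Forced set under Data Analysis: age, gender, race, ADL or IADL stage, proxy status. Neither term, and not insurance type either.
- Rule for further covariates: health conditions, living circumstances, stakeholder themes. Neither term is pre-specified.
- Aims 2, 3 and 4: neither term is added and no analysis by entry year is planned.
- Survey weights, drop-out weights and multiple imputation: these address sampling, non-response and missing values, not period or plan type.
- Sample size: similarity across the ten years is assumed, but only for the power calculation.

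So the omission is real.

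**2. The plan's pooled sample size.** 10 panels × about 4,000 = 40,000. From Table 5, 12,058 × 10/3 = 40,193. The stated 40,000 reproduces.

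**3. Cost of adjustment.** Nine entry-year indicators + one HMO indicator = 10 parameters per logit. The five-state outcome has four logits, so 10 × 4 = 40. The trichotomous Aim 2 outcomes have two, so 10 × 2 = 20.

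**4. Size of the confounding.** The documents give no trend in dissatisfaction or outcome and no HMO share. Everything in this step is an assumption, with no true effect inside any stratum. With stratum weight w, dissatisfied proportion d and 3-year mortality m, the pooled odds ratio is

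OR = [Σ w·d·m × Σ w·(1−d)·(1−m)] / [Σ w·d·(1−m) × Σ w·(1−d)·m].

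*Period:* ten equal panels, with linear falls from 16% dissatisfied and 12% mortality.

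| Fall in dissatisfaction | Fall in mortality | Spurious OR |
|---|---|---|
| 30% | 10% | 1.005 |
| 30% | 30% | 1.016 |
| 50% | 10% | 1.009 |
| 50% | 30% | 1.031 |

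In the last row, pooled mortality is 10.44% in the dissatisfied and 10.17% in the rest.

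*Plan type:* HMO share 15% to 25%, HMO-to-fee-for-service mortality ratio 0.8 to 0.9, dissatisfaction 10% versus 16% in either direction. The range is 0.974 to 1.022. The upper end has 25% in HMOs, ratio 0.8 and HMO members less dissatisfied. Among the dissatisfied, mortality is (0.25×0.10×0.096 + 0.75×0.16×0.12)/(0.025 + 0.12) = 0.0168/0.145 = 11.59%, against 11.37% in the rest. The lower end reverses the dissatisfaction figures.

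*Harsher generic check:* for a binary confounder with outcome ratio RR and prevalences p1 and p0 in the two exposure groups, bias = [1 + p1(RR−1)]/[1 + p0(RR−1)]. RR 1.1 with 20% versus 15% gives 1.020/1.015 = 1.005. RR 1.5 with 25% versus 10% gives 1.125/1.050 = 1.071.

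**5. Against the matching benchmark.** The illustration is an Aim 3 contrast, dissatisfaction on death. Table 4 gives detectable RRRs for death of 1.71 (dissatisfied versus neither) and 1.24 (satisfied versus neither). On the log scale the worst period case is ln 1.031/ln 1.71 = 0.0305/0.536, about 6% of the detectable effect. The match is approximate: Table 4 uses 1-year transitions and a three-level comparator, while the illustration uses 3-year mortality and two levels.

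**The case against.** The strongest defence is that the specification is still open. This is a research plan; an initial protocol with covariate definitions is due in month 9, variable specifications follow in Year 1, and stakeholder themes may add covariates. That is fair, and it makes the change easy. It does not supply the terms, because nothing in the plan commits to them.

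The second defence is that the bias is small on any reasonable inputs. That stands and limits how much weight the point can carry.

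Several stronger readings are tempting, and the documents do not support them:

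- *The bias is comparable to the smallest detectable effect, 1.07.* That figure is in Table 3 and concerns Aim 2, ADL stage 0 versus I. The illustration concerns Aim 3, where Table 4 applies. No Aim 2 bias has been calculated.
- *The plan itself says HMOs and Part D changed the study outcomes during the decade.* It links them to hospitalization, which is not one of the five transition states, and gives no date. A split at a particular policy year therefore has no basis in the documents.
- *HMO members are coded as Medicare only or other.* The plan does not say. Private-supplemental is equally possible, and any of the four levels would mix them with other coverage.
- *The stakeholders' question about a decade goes unanswered.* In context they ask whether 1-year results from three panels hold in the larger, adjusted analysis with 3-year follow-up. The planned Aim 3 models address that.

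**Conclusion.** The point holds as a minor one. Ten entry years and two plan types are pooled with no adjustment for either and no stated coding for HMO members. Confounding arises only if period or plan type relates to both the comparator and the outcome; that is plausible, not shown. The spurious ratio is about 0.97 to 1.03 under the specific assumptions above. It reaches 1.07 only in the generic check with an outcome ratio of 1.5 and a 15-point difference in prevalence. A reader should not infer that the main Aim 3 conclusions are at risk. The case for acting is that entry year is known by construction, HMO status has to be identifiable for the stated inclusion, and the adjustment is close to free.

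**What to change.** - Add panel entry year to the forced set under Data Analysis for the Aim 2 and Aim 3 models and for the regressions behind the Aim 4 simulations. Use nine indicators, or grouped years for rare outcomes such as institutionalization. Grouping also sits better with the plan's rule against analysing cells of fewer than 11 people.
- Add a separate fee-for-service/HMO indicator to the same set, or an HMO level to insurance type. If the latter, insurance type must itself be forced in. State how HMO members are coded, and confirm the field in the Access to Care files.
- In the simulations, hold entry year and plan type at each person's own values, as already planned for the other covariates.
- Do not make entry year a scored item in the Patient-Informed Surveillance Tool: future users will have no 2000-2009 value to enter.
- Optionally, report whether comparator effects differ between early and late panels. Label it exploratory, since it repeats across outcomes, horizons and staging systems, and do not use a 2006 cut-point.

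The plan describes all needed variables as being in the Access to Care files, so no new data source should be required. The cost is about 10 parameters per logit (40 in the five-state model) against about 40,000 people, plus a few lines in the protocol.

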#### **Outcomes:**

**Aim 2:** Comparators (see description below and in Table 2)

**Aims 3 and 4:** "no change" (individual remains at the same ADL/IADL stage), "functional improvement" (recovery to stage of less functional limitation), "functional deterioration" (reflected in higher ADL/IADL staging), "institutionalization" (long-term institutionalization), or "death."

**2. Quality Comparators (Outcomes for Aim 2 and exposures for Aims 3 and 4)**

Each quality comparator is made up of patient or proxy answers to several questions rated either as: "very satisfied, satisfied, dissatisfied, or very dissatisfied" or as: "strongly agree, agree, disagree, or strongly disagree" during the patient's baseline interview. Higher values will be coded to represent negative connotations. The comparators and component questions address: **Comparator 1: Care Coordination and Quality:** 5 questions on overall quality of care, information given, follow-up care, concern for overall health, and needs met at same location. **Comparator 2: Access Barriers:** 3 questions on availability of night/weekend, ease/convenience, and out-of-pocket costs. **Comparator 3: Technical Skills of PCP:** 3 questions about checking "everything", understanding medical history, and understanding what is wrong. **Comparator 4: Interpersonal Skills of PCP:** 4 questions about whether or not the PCP is in a hurry, does not explain, does not discuss, and acts like doing a favor. **Comparator 5: Quality of Information provided by PCP:** 4 questions about whether the PCP "tells all I

PRINCIPAL INVESTIGATOR (LAST, FIRST, MIDDLE): [name]

want to know,” “answers all my questions,” “has my confidence,” and dependence on doctor(s) to “feel better both physically and emotionally.” Combination of these questions into 5 comparator measures is supported by factor analyses with factor loadings of items on the 5 scores of 0.55 or greater. Cronbach’s coefficient alpha was 0.82 for global quality, 0.54 for access barriers, 0.89 for PCP technical skills, 0.79 for interpersonal manner, and 0.84 for Information giving. Average item-level responses will be determined for each variable. Comparators 1 and 2 will be available for all patients, but PCP comparators only for the approximately 90% of patients who have regular PCPs. Comparators will be presented trichotomously, addressing high and low quality extremes. For the access and quality comparators, the best and worse access and quality will be compared to the middle quartiles. For the PCP comparators, no PCP and quality in the highest quartile will be compared to the 3 lower quartiles similar to the approach taken by Lee and Casper.

Activity Limitation Stages determined during the baseline fall interview will be the key independent variable (see Table 1 for definitions). ADL stages (0-IV) will be primary and IADL stages (0-IV) analyzed secondarily. IADLs such as meal preparation are not always relevant when someone else is available to perform those tasks, yet IADL enables exploration of the effects of milder disabilities.

Other covariates: *Working age* 21 to 64 and 65 and over; *gender*; *race* (African American or Black, Hispanic, White, and other); *education* (high school graduation Y/N); *marital status* (married/unmarried); *income* (Medicare categories of annual household income from all sources); *insurance type* (Medicare only, Medicare and Medicaid-dual enrollee, private-supplemental, other (i.e., Champus, VA)); *living arrangement* (i.e., lives alone or with spouse only, with children, with other relatives or non-relatives, or in a retirement community); and the *presence or absence of accessibility features in the home* (home accessibility features). Health status will be captured by physician-reported *chronic conditions and impairments* (hypertension, asthma, diabetes, COPD, coronary artery disease, and congestive heart failure, intellectual and/or developmental disability, dementia or Alzheimer’s disease, neurological disorders, mental illness, no usable vision, and deaf). Building on our previous work, we know that the nature and severity of disabilities resulting from these conditions can be expected to vary. As example, neuropsychiatric conditions, particularly those causing intellectual disabilities, are often extremely disabling, while people who are blind or deaf often find ways to accommodate and perform basic activities. Analyses will control for residence based on Census regions.

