##### Choice of study design

In spite of spectacular advances, medicine and medical research at times exploit PWD. The biopsychosocial model informs this mixed methods Community-Based Participatory Research (CBPR) study where social and medical models of disablement are considered equally essential. Stakeholders input to the social model, while professional researchers input to the medical model (Figure 1). Consequently, we selected CBPR methods to ensure equal participation of stakeholders and clinician scientists in this work.

A parallel mixed methods design was chosen to combine strengths of qualitative and quantitative inquiry. Federally-funded investigators increasingly apply qualitative methods to understand beliefs. Integration of qualitative and quantitative methods

PRINCIPAL INVESTIGATOR (LAST, FIRST, MIDDLE): [name]

will link subjective (transformative) with objective (measurable) knowledge in ways that findings can be generalized to larger populations yet informed through the lens of diverse stakeholders.

Reflecting National Quality Forum (NQF) 3-step healthcare quality enhancement processes, stakeholders will explore how quality lapses (as measured by the 5 comparators) might change outcomes. The magnitude of actual quality lapses and the degree to which those lapses are associated with transition outcomes will be quantified. Stakeholders' interpretations of findings will inform policy simulations estimating maximum benefits to reducing gaps in quality according to each of the 5 comparators. The final deliverable will be a **Patient-Informed Surveillance Tool** through which the effects of healthcare system change on disparities and the wellbeing of PWD can be tested. All questions in the tool will be from the publicly available MCBS ensuring availability for immediate wide-spread implementation by health systems at project conclusion. Implementation of this tool by Medicare could have huge impact on the quality of care provided to millions of PWD. CBPR, in combination with broad dissemination efforts, is intended to engage patient, family, and clinician stakeholders to cause healthcare plans and PCPs to improve systems of care and services to PWD at the grass roots.

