The PCP quality comparators were less strongly related to 1-year transitions. Poorer PCP interpersonal skills were associated with functional deterioration (p=.01) and 1-year mortality (p=.003). Patients’ perceptions of poorer PCP interpersonal skills were marginally associated to institutionalization (p=.07). Poorer quality of information provision was related to institutionalization (p=.04). These findings provide powerful support for this study.

**Stakeholder interpretation:** Stakeholders found all findings logical except linkage between poorer perceived healthcare access and quality and functional improvement. They had the following thoughts and questions: Being angry with poor access and low quality healthcare might motivate functional improvement. Those who improved functionally might be more motivated to fight for better care. Will these findings persist after statistical adjustment and analyses across a decade and timeframe of 3 years? What other factors, potentially discoverable through stakeholder engagement, might explain this startling finding?

**AIM 1: Where do we see the problems?** Aim 1 seeks to uncover themes related to the 5 comparators and stakeholders’ perceptions on whether or not they experience healthcare and PCP quality problems and if those problems impact transition outcomes. PWD, PWOD, and families, in VAI and Urban groups, will address the following kinds of questions in a focus group format: *How does access and quality of healthcare received differ for PWD and PWOD? How does poorer quality healthcare impact risks of functional decline, institutionalization, or death?* The Clinician groups will address identical questions but relative to their clinical practices.

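### The three PCP comparators pool poorly rated PCPs with average ones, so the planned categories cannot show the effect of poor PCP care

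*Combined protocol and SAP*

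**What the plan says.** The section on Quality Comparators states the purpose of the coding: "Comparators will be presented trichotomously, addressing high and low quality extremes". For comparators 1 and 2 this is carried out: "For the access and quality comparators, the best and worse access and quality will be compared to the middle quartiles". For comparators 3 to 5 (technical skills, interpersonal skills and information from the PCP) the rule differs: "For the PCP comparators, no PCP and quality in the highest quartile will be compared to the 3 lower quartiles". The section cites an earlier study as precedent and gives no other reason for the difference.

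The same section says of the item scores: "Higher values will be coded to represent negative connotations". It also limits these three measures: "PCP comparators only for the approximately 90% of patients who have regular PCPs".

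Under Choice of study design, "stakeholders will explore how quality lapses (as measured by the 5 comparators) might change outcomes", and then: "The magnitude of actual quality lapses and the degree to which those lapses are associated with transition outcomes will be quantified". The sections on Impact on Health Care Performance and Importance of knowledge to be gained add, as targets, reduced confidence in PCP skills and groups receiving poorer PCP care.

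Under Data Analysis, Aim 2 models each comparator both in three categories and as a continuous score, with the comparator as the outcome. Aim 3 asks whether people who rate their PCPs highly have fewer bad transitions. Aim 4 uses regression coefficients to simulate an optimal level of each comparator.

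**The concern.** The low extreme that the coding is meant to capture has no level of its own for three of the five comparators. The only level on the low side is having no PCP, which is the absence of a provider rather than a poor rating of one. People with a poorly rated PCP are averaged into the reference.

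The lapse question is about exactly these people. The decision points in Table 2 include whether a PCP who interacts badly will affect functioning. The Preliminary findings report that poorer interpersonal skills were associated with deterioration (p=.01) and one-year mortality (p=.003), although the coding behind those results is not given.

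The policy message is at stake. A benefit of outstanding PCPs and a harm from poor PCPs call for different action, and the planned contrast cannot tell them apart. Aim 4 then sets the PCP scenarios beside care-quality and access scenarios whose low extreme is modelled.

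**Working it through.** The plan gives no power or effect figure for a PCP comparator (Tables 3 and 4 cover comparator 1 only), so there is no figure to reproduce. The check is of structure.

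**1. Levels side by side**

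| Comparators | Low level | Reference | High level |
|---|---|---|---|
| 1 and 2 | worst | middle quartiles | best |
| 3 to 5 | no PCP | three lower quartiles, including the worst | best |

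**2. What best versus the rest reveals.** Let b be the RRR for best versus middle, w the RRR for worst versus middle, and s the share of worst-rated people in the pooled reference. For a rare event the reported RRR is R = b / [1 + s(w − 1)]. With exact quartiles s = 1/3, so R = b / [(2 + w)/3]. The values of b and w below are assumed.

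- Harm only in the worst group (b = 1): w = 1.5 gives R = 1/(3.5/3) = 0.857, and w = 2 gives R = 1/(4/3) = 0.75. Without the rare-event approximation, for middle-group odds of 0.02 to 0.20, R is 0.858 to 0.864 and 0.752 to 0.769.
- Working back from R = 0.80, b = 0.80 × (2 + w)/3. Hence w = 1.00 goes with b = 0.80, w = 1.50 with b = 0.93, and w = 2.00 with b = 1.07.

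One reported figure therefore fits no harm from poor PCPs, or a doubling.

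**3. Aim 4.** Take b = 1, w = 1.5 and exact quartiles. The mean relative level in the lower three quartiles is (1 + 1 + 1.5)/3 = 1.167. Moving everyone to best multiplies this by 0.857, and 1.167 × 0.857 = 1.00, which is the correct average. Individually, the true gain is 0 in the two middle quartiles and 0.5 in the worst, while the model gives each 0.167. The total is right (3 × 0.167 = 0.5) and its allocation is not. A disability stage whose worst-rated share differs from the average can be given too small or too large a gain. Table 9 promises results by stage.

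**4. Size of the worst-rated group.** Table 5 expects 40,000 people over ten panels, and 40,000 × 0.90 = 36,000 have a PCP.

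- Exact quartiles (assumed): 36,000/4 = 9,000 worst-rated, in a reference of 27,000.
- Split like comparator 1 at stage I, which the Sample size section gives as 13.32%, 60.19% and 26.49% (assumed to carry over): 36,000 × 0.1332 ≈ 4,800 worst-rated. Their share of the non-best group is 13.32/(13.32 + 60.19) = 18%. With s = 0.181, b = 1 and w = 1.5, R = 1/(1 + 0.181 × 0.5) = 0.92.

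**5. Precision of a separate worst contrast.** Comparing 9,000 worst with 18,000 middle as two proportions (80% power, two-sided 5%), the detectable RRR is about 1.39, 1.27, 1.17, 1.12 and 1.10 at assumed event proportions of 1%, 2%, 5%, 10% and 15%. This leaves out design effect and attrition, so it is optimistic. The plan's own figures for a low category, Table 4 for comparator 1, are 1.71 for death, 2.71 for institutionalization and 1.50 for deterioration. For the high category they are 1.24, 1.63 and 1.16.

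**The case against.** A reader might infer that the PCP comparators cannot answer the study's question at all. The documents do not support that. Aim 3 is worded around highly rated PCPs, and best versus the rest tests that wording. Lower quality in a relative sense is also addressed. What is missing is the separation of poor from average. In Aim 2 the continuous score uses the full range, but there the comparator is the outcome, so it says nothing about transitions.

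A reader might also infer that the Aim 4 population benefit is understated. Step 3 shows that it need not be. Stage-specific results can be off, but by how much cannot be stated, because the documents do not give PCP ratings by stage.

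Nor can one say that a third of the reference is poorly rated. The scores average three or four four-point items, ties are likely, and the only split shown would make it about 18%.

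The coding is deliberate and has a cited precedent. That source is not available here and may contain a reason. It would still not reconcile the coding with the purpose stated in the same paragraph.

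Aim 3's own text does not fix the exposure form, so a continuous PCP score might be intended. It is not stated, and the only exposure form described for Aims 3 and 4 is the three-level one.

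Finally, since higher scores are negative, the highest quartile could be read as the worst. The phrase refers to quality, and the Sample size section orders comparator 1 from dissatisfied to satisfied, so best is the natural reading. On the other reading the best-rated PCPs would be pooled, and one extreme would still be lost.

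**Conclusion.** The point holds in limited form and is worth a change. For three of five comparators the stated categories do not capture the low extreme, and no stated categorical analysis separates poorly rated from average PCPs. The goals on lapses and poor care are therefore unmet for those comparators, although Aim 3's wording about highly rated PCPs is served. A best-versus-rest RRR cannot distinguish benefit at the top from harm at the bottom: with exact quartiles, 0.80 is compatible with a worst-versus-middle RRR anywhere from 1.00 to 2.00 as b runs from 0.80 to 1.07.

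In Aim 4 everyone in the lower three quartiles receives the same gain. This can blur stage-specific results and makes the PCP scenarios not like-for-like with comparators 1 and 2.

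The structural conclusion needs no assumption beyond reading the highest quartile as best quality. The sizes do rest on assumptions: the values of b and w are illustrative, and the worst-rated group of about 4,800 to 9,000 depends on how the scores split.

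**What to change.** Code comparators 3 to 5 with four levels in Aims 2, 3 and 4: no PCP, worst-rated group, middle group (reference) and best-rated group. Set the cut points after checking ties in the item averages. Alternatively, add the PCP score as a continuous exposure in Aims 3 and 4 among people with a PCP. In either case, state that the highest quartile means best quality, because the scores run the other way.

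The data are already requested. The cost is one extra level per PCP comparator and a smaller reference for the best contrast (about 18,000 instead of 27,000 with exact quartiles). The precision of the new worst contrast may also be limited. If it resembles the low category in Table 4, an RRR of 1.5 would be at the limit for deterioration and below what is detectable for death and institutionalization. The plan should say so and report the estimates with their intervals.
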